Aim 2 of this study is to estimate the impact of M&M on agitated and aggressive behaviors in NH residents with moderate to severe dementia. Agitated and/or aggressive behaviors are measured three ways: by interviewing staff about resident behaviors over time (primary outcome); through direct observation of residents when using and not using M&M (secondary outcome); and using available administrative data (secondary outcome). Other secondary outcomes include: other emotional states directly observed while the resident is using and not using M&M (anger, pleasure, alertness, sadness), antipsychotic use, antidepressant use, anxiolytic use, and depression. In this cluster RCT, the unit of random assignment is the facility, but the unit of analysis is the patient, clustered within the facility. The analytic approach we propose is based upon the cumulative likelihood of reductions in agitated and aggressive behaviors in a long-stay population with moderate to severe dementia, conditional upon survival to at least one post-intervention observation. Outcomes will be evaluated using a repeat parallel design, comparing wave 1 (intervention) and wave 2 (control) NHs (n=54) in the first study year, and wave 2 (intervention) and wave 3 (control) NHs (n=54) in the second study year. The repeat design allows for modification of the intervention delivery between waves to increase adherence. Since we do not expect the intervention to affect mortality, the comparison will be based on the last observed total agitation score among residents meeting eligibility criteria in the treated and control groups. All deaths among exposed and control populations will be routinely controlled and reported to the data safety and monitoring board for monitoring purposes. Facilities will be stratified by corporation, and balanced on baseline agitated and aggressive behaviors and number of eligible residents, prior randomization. Because we are interested in the effect of the intervention among those who use it, we will also conduct an as-treated analysis, using a technique described by multilevel-mixture analysis for analyzing cluster randomized data with non-compliance.

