5 STUDY INTERVENTIONS

5.1 Interventions, Administration, and Duration

The M&M personalized music program will be implemented for at least 8 months in each intervention facility. (Obviously, facilities are encouraged to continue to use the music devices with patients long after this 8-month period and the devices will remain at the facility for use among appropriate patients). The intervention consists of: 1) identifying the music a resident with ADRD preferred when she was between the ages of 18 and 24, either by consulting family members or through trial and error; 2) creating a personalized playlist for each resident; 3) loading this personalized playlist on the resident's music player (iPod); and 4) using the iPod with the resident twice a day for approximately 30 minutes to 1 hour per use, at times when residents with ADRD tend to experience BPSD. Recommended times are when the resident gets up in the morning (during daily personal care) and in the late afternoon, when sundowning is common. In addition to these set times, NH staff are encouraged to use the music at other times when an individual resident is likely to experience BPSDs. In the first parallel trial. NH staff will be responsible for completing all four steps. In the second parallel trial. research staff will create personalized playlists (step 2) and load music players (step 3). For the second parallel trial, staff will provide Brown with 15 eligible residents' "preferred" music genre and resident age. Brown research staff will preload iPods with popular music in the resident's preferred genre from when they were between the ages of 16 and 26 (current best practice recommendation). This process is similar to playlists generated by Spotify and other streaming services. Additionally, we will be using playlists from the first trial to culturally and regionally tailor music selections. This is particularly important for the current study as we have four regionally and racially diverse corporations: two NH corporations serving predominately white, rural

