Certification and Survey Provider Enhanced Reporting (CASPER): CASPER are publicly-available data from the Medicare/Medicaid certification and inspection process that all NHs undergo. Brown investigators have assembled a three-decade data panel on all certified U.S. facilities including data on ownership, size, staffing, services, patient acuity, and quality inspection results.(81, 82)

Primary Data

Primary data collection tools can be found in Appendices B-H. These data will be collected by independent data collectors during three site visits (baseline, four, and eight months).

iPod Metadata: The iPod shuffle retains limited data about use. Information about the songs played (e.g., artist, album, track title, duration of track, genre) and the number of times a song is played are available and will be downloaded.

Staff Interviews: the RAs will interview the NH caregiver most familiar with the resident using the Cohen Mansfield Agitation Inventory (CMAI), a validated 29-item tool for measuring agitation in people with ADRD living in NHs.(83, 84) We will use the CMAI to assess the frequency and severity of eligible residents' behaviors over the previous week.

Resident Observation (Trial 1 Only): The Agitated Behaviors Mapping Instrument (ABMI) will be used to observe resident behaviors at the point of intervention. Using independent, trained observers, we will observe

the frequency of residents' agitated behaviors over short intervals, when they are using and not using the M&M intervention. We will also use the Lawton Observed Emotion Rating Scale (OERS),(85) which was designed to measure pleasure, anger, anxiety/fear, sadness, and general alertness. Reactions to music will be captured, when observations include the use of M&M.

Implementation Observation Checklist: The Implementation Observation Checklist is completed by data collectors while on-site. It describes adherence to specific aspects of the study protocol (e.g., are the playlists individualized, are the iPods labeled, are frontline staff involved in delivering intervention to residents, etc).

Key Informant Interviews: Key informant interviews with the administrator and nursing lead in each intervention facility will be completed by Brown research team members at 4- and 8-months (mid- and full-implementation). These interviews will identify facilitators, barriers, and best-practices related to implementing the M&M program, and feedback on corporate trainings.

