Off-Site (Day 1): All on-site data collection is completed assuming internet at NHs is not available or reliable. In the evening, between the first and second days, the data collector needs to: upload completed staff interviews in Qualtrics, and upload metadata to server.

On-Site (Day 2): The second day is dedicated to systematic observation of the residents, while using and not using the music. When the data collector returns the second day, she should notify the administrator or contact person that she is on-site and asked to be introduced to the nursing staff on the unit(s) where the observations will take place. Each of the residents will be observed at least 4 times during the day.

During the baseline visit none of the residents will have received the intervention. All observations will be of residents without the iPods. At the 8 month visit, all of the residents should have received the intervention and observations will be of residents while using and not using the iPods. At least four observations will be conducted for each resident: one in the morning; one mid-day; one in the late afternoon; and one with music (if music is being used for resident, else at a time chosen by data collector). At least one of the observations has to be during a meal. Residents will not be observed during any activities in which personal modesty is compromised (e.g., dressing or bathing). Whenever possible, residents will be observed in common areas, but may also be observed in their rooms with the door open or ajar. The evaluator should stand at an inconspicuous distance from the resident (minimum 5 feet from resident).

Off-Site (Day 2): All on-site data collection is completed assuming internet at NHs is not available or reliable. In the evening, after the second day, the data collector needs to: upload completed observations in Qualtrics and complete the implementation observation. The implementation observation captures direct observations of how the equipment is being stored and used by staff, and gestalt impressions of staff familiarity and buy-in. The implementation observation will be completed by the evaluator immediately after leaving the site on the second day.

All other data are derived from existing data. Please see Section 6 which details these sources.

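### Trial 1 direct-observation outcome (ABMI, OERS): a contrast of music and no-music moments is confounded by timing and indication, and no matching or adjustment is planned

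*Combined protocol and SAP*

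**What the plan says.** **Outcome.** The Précis (Aim 2) and Section 6 measure agitation and aggression "through direct observation of residents when using and not using M&M (secondary outcome". Section 6.1 says that the ABMI records behaviours over short intervals "when they are using and not using the M&M intervention", adds the OERS for emotional states, and limits both to Trial 1.

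**When music is given.** Section 5.1 asks for two sessions a day "at times when residents with ADRD tend to experience BPSD". It continues: "Recommended times are when the resident gets up in the morning (during daily personal care) and in the late afternoon, when sundowning is common". Beyond those times, "NH staff are encouraged to use the music at other times when an individual resident is likely to experience BPSDs".

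**When residents are observed.** Section 10.1 (On-Site, Day 2) lists "one in the morning; one mid-day; one in the late afternoon", and then "one with music (if music is being used for resident, else at a time chosen by data collector". It adds: "At least one of the observations has to be during a meal". Activities that compromise modesty, such as dressing and bathing, are not observed. No resident has music at the baseline visit.

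**Analysis.** Section 9.5 gives an intention-to-treat model and a complier model for the CMAI. It gives none for the ABMI or OERS.

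**The concern.** Music is given because symptoms are present or expected, while most observations follow the time of day. A moment with music and a moment without it can then differ in underlying agitation before the music has acted.

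The fourth observation brings a related problem into any comparison of arms. For a music user it falls at a session that staff timed. For a control resident, or a non-user in an intervention home, it falls when the data collector chooses.

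This is the trial's direct measure of agitation and mood at the point of use. If the contrast is reported as an effect of music, a timing difference could be mistaken for benefit or could hide it.

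**Working it through.** **1. Is there a stated figure?** Not for this outcome: the documents give no effect size, power or agitation level by time of day for the ABMI or OERS. The 24 homes per arm in Section 9.2 concern the CMAI. They reproduce with 15 residents per home (405/27 in Table 1): 2(1.960 + 0.842)² × 20²/6² × (1 + 14 × 0.12) × (1 − 0.5²) = 350.6 residents per arm, and 350.6/15 = 23.4, rounded up to 24. This has no bearing on the present point.

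**2. The two schedules side by side.**

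| Part of day | Music (5.1) | Observation (10.1) |
|---|---|---|
| Morning | Recommended, on rising, during personal care | One slot; dressing and bathing not observed |
| Mid-day | Not a recommended time | One slot |
| Late afternoon | Recommended | One slot |
| Other | When staff expect symptoms | Fourth: at a music session, or when the collector chooses |
| Meal | No rule | At least one observation, with or without music |

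Two of the three slots share a part of the day with recommended music use. Three differences remain: the mid-day slot, the part of morning care that cannot be observed, and the staff's choice of moment. Sharing a part of the day does not match the resident's state. The slots are also not declared music-free, so the not-using condition is not fully defined.

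**3. Illustration on a ratio scale (assumed values).** Let *e* be the true proportional reduction and *k* the untreated agitation at music times divided by that at the comparison observations. The observed ratio is *k*(1 − *e*). Take *e* = 1/3, so the true ratio is 0.67.

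- No overlap, *k* = 1.25, 1.5, 2.0: observed 0.83, 1.00, 1.33.
- With overlap: suppose morning and late-afternoon slots are as agitated as music times, and agitation at those times is *K* times the mid-day level. Then *k* = *K* / [(2*K* + 1)/3] = 3*K*/(2*K* + 1). For *K* = 1.25, 1.5, 2.0, *k* = 1.07, 1.125, 1.20 and the observed ratio is 0.71, 0.75, 0.80. The true 33% reduction reads as 29%, 25% or 20%. Here *k* cannot exceed 1.5, so the sign cannot reverse.
- If mid-day (or a meal then) is the more agitated time, say *K* = 0.8, then *k* = 2.4/2.6 = 0.92 and the ratio is 0.62. The benefit is then overstated.

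**4. Illustration on an additive scale (assumed values).** Let *a* be the excess agitation at music times in SD units, *f* the share of no-music observations at equally symptomatic times, and *e* the true effect. The contrast is *e* + *a*(1 − *f*). With *e* = −0.3:

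| *a* | *f* = 0 | *f* = 1/3 | *f* = 2/3 | *f* = 1 |
|---|---|---|---|---|
| 0.2 | −0.10 | −0.17 | −0.23 | −0.30 |
| 0.5 | +0.20 | +0.03 | −0.13 | −0.30 |

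At *f* = 2/3, the value nearest to the overlap in step 2, between 0.07 and 0.17 of the 0.30 SD benefit is hidden.

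**5. Pooling all four observations by arm.** Suppose every intervention resident has a music observation, at a time *a* SD more agitated than the collector-chosen time in controls. Averaging four observations then adds *a*/4 to the arm difference before any effect of music: 0.05 SD for *a* = 0.2 and 0.125 SD for *a* = 0.5.

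**The case against.** The strongest reply is that the plan never specifies a same-day, within-resident comparison. The outcome text says when residents are observed, and the Précis says that outcomes will be evaluated by comparing intervention and control homes. This stands: a reader might infer that a biased within-resident contrast is the planned analysis, but no ABMI or OERS analysis is written down. Yet the outcome is repeatedly defined by music status at the moment of observation, and that definition leads directly to the confounded contrast.

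The schedule is also less mismatched than it may look. A reader might take the slots as fixed clock times, free of music, with the meal tied to the no-music condition. They are parts of the day, their music status is not stated, and the meal rule covers any observation. The overlap with recommended music times limits the bias, as step 3 shows. It does not remove it.

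A further inference would be that staff offer music only to calm residents, so that the contrast flatters the music. Nothing supports this, and Section 5.1 points the other way.

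Finally, Section 10.1 calls itself an overview and refers to a Manual of Procedures, and the ABMI form in Appendix C is not reproduced. Timing or meal rules may be there. That could narrow the gap in the observation procedure, but it would not supply the missing ABMI/OERS analysis.

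**Conclusion.** The point holds as one about identification. With music directed to likely symptoms, the fourth observation chosen differently by exposure, and no matching or adjustment, neither a using/not-using contrast nor a pooled four-observation comparison of arms isolates the effect of music.

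The size is not known. The figures above rest on assumed agitation levels and only show that plausible imbalances matter. With the overlap allowed for, they attenuate a true benefit (33% read as 20% to 29%, or −0.30 SD read as −0.23 to −0.13) rather than erase it. A reader might infer that the benefit would be lost or reversed. That needs *k* of 1.5 or more, which the overlap makes less likely and the documents do not show. The direction could also differ if the no-music or meal observations are the more agitated ones.

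Nor does it follow that the trial cannot be interpreted. This is a secondary outcome in Trial 1 only. The CMAI primary outcome is unaffected, and the three scheduled slots allow a randomised comparison free of this problem.

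**What to change.** Add an ABMI/OERS section to the statistical plan:

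1. **Effect analysis.** Compare randomised arms on the three scheduled-slot observations at 8 months, whether or not music is in use at that moment. Adjust for the same slot at baseline, account for clustering by home, and leave out the fourth observation.
2. **Using/not-using contrast.** Report it only as a descriptive point-of-use association, adjusted for part of day and, where recorded, meal. Adjustment does not remove the staff's choice of moment, so it should not be called an effect of music.
3. **Slot definition.** Section 7.4 allows at most four observations per visit and Section 10.1 requires at least four. Reconcile the two and state which observation fills each slot.

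**Cost.** Analysis text only. Section 9.2 indicates that the first trial is complete, so the observation schedule cannot change. Table 1 shows primary data collection in Sequence 1 and Sequence 2 homes in Period 1. Section 10.1 describes observations at baseline and 8 months, and I read its slot list as applying to both visits. The amendment should be dated and should say whether the observation data had already been examined by arm.

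**Downside.** There is one fewer observation per resident, and the randomised comparison estimates the effect at scheduled times rather than at the point of use.

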10.2 Data Confidentiality

Brown University's Center for Gerontology and Health Care Research will receive EMR patient-level data from partnering nursing home corporations. All four NH corporations have integrated sophisticated EMR systems in their facilities. The NH networks already have experience extracting MDS from their EMR systems for purposes of submitting mandatory, regular MDS reports to CMS. To protect patient confidentiality, the two corporations will place their data in a SSH secure server and will provide login information to Brown University. Data transfer to Brown University secure servers will be via SFTP protocol with password protection. Once the files have been uploaded to Brown University's servers they will be stored, unmodified, in a secure file location specific to these uploads. They will then be read into SAS datasets, one per file type. Brown University will then notify the facilities that the data was successfully downloaded and extracted, at which point the facilities will remove the data from their servers. All data files will be accompanied by a manifest detailing the number of distinct persons and records expected in them. Brown University will connect to the corporation servers on a monthly basis. Identifiers such as HICs and SSNs, will be included in order to be able to merge these person-level data to the data received from CMS. Brown University's information systems manager will be in charge of

the data transfer, and he will replace the HICs and SSNs fields with a Brown University-generated identification number (throughout our different data sources) to allow linkage of data for analytic purposes.

10.3 Data Management

Brown University's Center for Gerontology and Health Care Research will serve as the Data Management/Statistical Center for the METRICAL trial. The Center will be responsible for: receiving all data from CMS (Medicare, MDS), receiving all EMR data from study facilities, linking all secondary data with primary data collected onsite, and creating an analytic file and conducting analyses. Brown University investigators and database management staff already receive national MDS, Medicare, and OSCAR data semi-annually or quarterly under several CMS DUAs. There is a well-established data base management structure to linking these files. Brown also has experience linking EMR data from facilities with CMS Medicare claims and the MDS. The integration will be easily achieved thanks to the availability of HIC and SSN personal identifiers in both the EMR data from facilities and in the CMS Medicare claims and MDS data.

10.4 Data Use Agreements

The Brown University Center for Gerontology has an extensive history of working with ResDac to obtain DUAs to use CMS MDS and Medicare data for NIH funded projects, which will be obtained for this project. Our team will ensure all DUAs are compliant with NIH requirements.

11 PARTICIPANT RIGHTS AND CONFIDENTIALITY

11.1 Institutional Review Board (IRB) Review

The METRICAL protocol was reviewed and approved by the Brown University Institutional Review Board (IRB).

Informed Consent Forms

The Brown IRB approved two waivers of individual consent. The Brown Institutional Review Board (IRB) approved a waiver of informed consent for secondary data under 45 CFR 46.116. This waiver covered the obtainment and linkages of EHR, MDS, Medicare Enrollment and Vital Status Data, and iPod metadata. The Brown IRB also approved a waiver of informed consent for the proposed primary data collection under 45 CFR 46.116. This made it possible to collect primary data for all eligible residents, and to link staff interview and direct observation data to the available secondary data.

11.2 Participant Confidentiality

The main risk to participant confidentiality is a breach of confidentiality with the use of identifiable data. All research staff involved in the study will receive training in the protection of human subjects. The procedures described here address our efforts to minimize the risk of breach of confidentiality. All data management and analyses will be conducted by the Brown Center for Long-Term Care Quality & Innovation (Q&I Center), which is administratively housed within the Center for Gerontology & Healthcare Research and which leverages Gerontology's administration and computing infrastructure. Researchers and staff have many years of experience working with identifiable data files on a large scale and have numerous security measures in place to ensure the integrity and confidentiality of the data. CMS data will be covered under the strict terms of a data use agreement (DUA). The CMS DUA will ultimately cover MDS, enrollment, and Vital Status File data. Though not required since HIPAA waivers cover the release of the resident data from the NH corporations to Brown University, if requested, we will also enter into DUAs with each of the NH corporations detailing the appropriate use of data. We will submit all executed DUAs to the IRB.

At the conclusion of this study, or by the date of retention identified in the DUA, a CMS "Certificate of Disposition" certifying the proper destruction of all data obtained from CMS will be sent to CMS. All non-CMS data will be handled in a similar restrictive manner. In addition, all output containing individual identifiable information is treated as confidential data. This information is never transferred electronically via email. Shredders are used on any printed material containing individual identifiers. We will ensure that systems are in place to minimize the risk of breach of confidentiality for all data in this trial. Brown maintains numerous confidential databases, including MDS and Medicare files, and has a high level of security built into its computing systems. We will work closely with NH corporate leadership to develop protocols to maintain a high

level of data confidentiality for extracting and merging data from their EHRs. As mentioned above, the Q&I Center leverages Gerontology's administration and computing infrastructure. Gerontology maintains numerous confidential databases and has a high level of security built into its computing system. All data received at the Center will be stripped of any HIPAA personal identifiers and assigned unique identifiers. Access to the crosswalk between personal identifiers and new unique identifiers is restricted to the systems manager, [name], and this information is maintained in very high-security data files. No analytic files will contain personal identifiers.

The procedures described here address our efforts to minimize the risk of breach of confidentiality. First, all staff involved in the study receive training in the protection of human subjects. Second, Brown University researchers and staff have many years of experience working with data files on a large scale and have numerous security measures in place to ensure the integrity and confidentiality of the data. We treat all output containing individual identifiable information as confidential data. This information is never transferred electronically via email or other protocols. Shredders are used on any printed material containing individual identifiers.

We maintain numerous confidential databases and have a high level of security built into our computing system. The computing infrastructure consists of a VMS cluster, which houses all substantial data, a group of Windows servers that provide computing services and infrastructure support for client systems, and client Windows PCs through which all users access our systems. Network security is provided by a combination of firewalls, local network access controls, and continuous auditing and monitoring for security breaches. All access from systems external to the LAN is limited to encrypted channels (e.g., SSL for VMS terminal sessions or VPN connections for LAN file sharing access). Unencrypted access is provided only for the CGHCR external Web site and general e-mail support functions. The VMS cluster acts as a file server for Windows clients, and file access controls are consistently applied whether access is from the VMS or Windows environment.

Security within the system is applied via Access Controlled Entries (ACEs) attached to all files on all systems. Security is applied uniformly to all files within a subtree of any file system, with the general rule that groups of users sharing a common task may read each other's files but, in most cases, not write to each other's files. VMS provides a highly-secure programming environment with ACEs applied to all objects and extremely controlled access to the larger system for individual users, as well as a versioning file system, secure batch queues and distributed processing, and efficient backup and recovery procedures. Windows clients are limited to a subset of these services (e.g., there is no way for file version information to be shown to Windows clients), but otherwise access is secured as for any other method of accessing data.

Personally- and partially-de-identified data are housed in files that are restricted to systems management or to programmers who have been identified as custodians. No data are ever moved to more "public" spaces without identification information being stripped or non-reversibly encoded. Encoding is generally done via fairly large Roman cyphers applied iteratively to the original character string. No reverse encoding is ever generated nor maintained. Any matching between personally-identified data sources is done within a secured area prior to any data being exported. Windows servers that house partially de-identified data have matching ACEs applied so that access restrictions are applied consistently with VMS-based data.

Since we use demographic covariates for many of our analyses, even the encoded data are best considered partially de-identified. ACEs restrict access to all data housed by CGHCR, such that access to any data elements on the servers is limited to those staff authorized to make such access. Authorizations are, in turn, granted by the core system's support staff upon request from a PI or other appropriate data owner. All users authorized to access CGHCR systems have access to some storage that is considered "general file sharing" but, by convention and policy, all individual or otherwise restricted data is prohibited from being stored on such space. Desktop systems are authorized to specific users, and it is assumed that they will store data they are authorized to work with on such local systems. The LAN is switched, yielding a reasonable amount of security between clients and servers within the LAN. Desktop systems are required to run current anti-virus software and are prohibited from running local file-sharing software. External analyses are run periodically to verify the security of systems within the LAN.

Similarly, the Windows servers which support the LAN are configured as a local, isolated, secure, collapsed AD forest local to our LAN. DNS, DHCP, and other critical services are secured within the context of the local forest and are not accessible externally (with the exception, of course, of VPN or RDP access from authorized client systems). Extensive monitoring is done from the VMS cluster to ensure the health and stability of the Windows forest structure, and the individual servers within it.

In summary, CGHCR's VMS computer system is highly secure and accessible only to authorized users. Within the group of authorized users, access to project data is restricted to individuals who are authorized to work on that specific research project. Access to identifiers is further restricted to the systems manager alone. Furthermore, CGHCR employees have signed an oath of confidentiality, and its violation is sufficient grounds for immediate termination.

